Subjects will fly from Eugene, OR to Denver, CO and be driven from Denver to the field site (~10,000 ft) where they will be housed and fed for 2 weeks. Upon arrival, subjects will fill out AMS questionnaires and have saturation measured. Prior to departure from Eugene, a research staff member will meet subjects at the airport and they will be given a telemetric core temperature pill to take 5-10 hours prior to the 5k time trial in Colorado. If subjects do not take the pill the night prior to exercise testing, they will have to take the temperature pill as a suppository before testing. After, subjects will run the 5k time trial, perform cognitive function tests, and then will be taken to preview the course for the rucksack carry to be performed on day 2. Dried Blood Spot samples will be taken utilizing a commercially available dried blood spot sampling device (80 uL) (TASSO, Tasso Inc, Seattle, USA). Dried blood will be analyzed for HGB, CD71/Band3, ESAs, and reticulocytes. In the evening, subjects will have an IV placed and venous blood drawn, and will perform Hb mass & p50 measurements (10 mL blood draw). Venous blood (60 mL) will be analyzed for various biomarkers. Total blood drawn for this day of ~71 mL. Subjects will fill out AMS questionnaires and have saturation measured before going to sleep. Any subject with child bearing potential will be required to take a pregnancy test on this day.

On day 2, AMS scores will be taken and saturation measured (morning and night), and subjects will participate in the rucksack carry. Cognitive function will also be measured.

On day 3, AMS scores will be taken and saturation measured (morning and night). Cognitive function will also be measured.

Subjects will also undergo ultrasound measurements and have resting ventilation and HCVR measured on either day 2 or 3.

Mid high altitude measures: Days 7-8

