On day 7, AMS scores will be taken and saturation measured (morning and night), and subjects will run the 5k time trial, perform cognitive function tests, perform Hb mass & p50 measurements (10 mL blood draw), and have venous blood drawn (60mL). Venous blood will be analyzed for various biomarkers. Dried blood spot samples will also be taken (80 uL). Total blood drawn for this day of ~71 mL. This day will be a repeat of day 1 at altitude. Any subject with child bearing potential will be required to take a pregnancy test on this day. Subjects will be given a telemetric core temperature pill to take 5-10 hours prior to the 5k time trial on day 7/8. If subjects do not take the pill the night prior to exercise testing, they will have to take the temperature pill as a suppository before testing.

On day 8, subjects will participate in the rucksack carry.

Subjects will also undergo ultrasound measurements and have resting ventilation and HCVR measured on either day 7 or 8.

Late high altitude measures: Days 13-14

On day 13, AMS scores will be taken and saturation measured (morning and night), and subjects will undergo ultrasound measurements, run the 5k time trial, perform cognitive function tests, perform Hb mass & p50 measurements (10 mL blood draw), and have venous blood drawn (60mL). Dried blood spot samples will also be taken (80 uL). Venous blood will be analyzed for various biomarkers. Total blood drawn for this day of ~71 mL. This day will be a repeat of day 1 at altitude. Any subject with child bearing potential will be required to take a pregnancy test on this day. Subjects will be given a telemetric core temperature pill to take 5-10 hours prior to the 5k time trial on day 7/8. If subjects do not take the pill the night prior to exercise testing, they will have to take the temperature pill as a suppository before testing.

Subjects will also undergo ultrasound measurements and have resting ventilation and HCVR measured on day 13.

On the morning of day 14, subjects will participate in the rucksack carry. Subjects will be driven back to Denver, CO where they will fly back to Eugene, OR.

Post-altitude measures, Eugene, OR

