Within 1 week of returning to Eugene, OR, subjects will return to the Cardiopulmonary Lab (Eugene, OR) to repeat the 5k run and blood draw only. Tests will be performed over post-Altitude days 3-5. The 5k run will be done either on the same day as the other tests, or on a separate day depending on subject availability. Total blood draw 60 mL.

Note: During the 14 days at high altitude, subjects will be involved in data collection on days 1, 2, 3, 7, 8, 13 and 14. On all other days, there will be group activities and the possibility for subjects to hike or bike ride in small groups. They will not participate in any research activities during these “off” days, and they will be reminded frequently to follow CDC guidelines for COVID-19 risk mitigation (see ‘COVID-19 exposure scenario’ below).

Description of Data Collection Procedures:

Pulmonary Function Tests: Subjects will perform standard non-invasive spirometry to measure a maximal inspiratory and expiratory flow-volume loop, forced vital capacity (FVC), slow vital capacity (SVC), forced expiratory volume in 1 sec (FEV1), and mid expiratory flow (FEF25-75%). These tests will require the subject to blow in and out of a mouthpiece connected to a computerized flowmeter (pneumotachometer). This is a routine clinical test.

VO_{2max} tests: The VO_{2max} test will be an incremental test to volitional exhaustion on a cycle ergometer. Subjects will breathe through a mouthpiece and will begin cycling at a low resistance (50 W), with the resistance increasing every minute by 25 W. The test will continue until the subject reaches volitional exhaustion or a plateau in VO₂ as measured by our metabolic cart (Medgraphics Ultima CPX) is reached. During the entire protocol, subjects will breathe room air through a 2-way non-rebreathing small sampling flowmeter (pneumotachometer), which will allow us to measure

ventilation (V_E), VO_2 , and breath-by-breath metabolic data. Subjects will be instrumented with a forehead oxygen sensor to measure heart rate and SpO₂ at rest and during exercise.

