hematocrit, baseline proportion of hemoglobin bound with CO (HbCO), and baseline proportion of hemoglobin bound with oxygen (HbO₂). HbCO is typically 1.5 to 2.0% in nonsmoking city dwellers. Once the baseline blood sample has been taken, subjects will be instructed to breathe out completely. Then they take a slow breath from the rebreathe circuit prefilled with 100% oxygen to completely fill their lungs while a bolus of 99.9% pure CO is injected into the circuit. The bolus volume of CO is calculated from body mass (1.0 mL/kg body mass for men; 0.8 mL/kg body mass for women). This dose of CO is expected to raise HbCO by ~6% to ~8%, which is below the levels associated with side effects (>15%; see below). After CO administration the subjects begin breathing normally for 10 minutes. At the end of this 10-minute period, subjects expire all of their air back into the spirometer and the spirometer is sealed and a post-rebreathe blood sample of 2mL is taken to measure the above-mentioned blood parameters (with the exception of p50, which is measured once prior to Hb mass testing). Subjects then goes back to resting while breathing ambient air. Finally, we obtain the total volume of gas in the rebreathe circuit and determine the concentration of CO left in the rebreathe circuit after the test. Using established formulas, we calculate hemoglobin mass and then use the following equations to obtain red cell volume (Red Cell Volume = hemoglobin mass x hematocrit x hemoglobin-1 x 100-1) and then blood volume (Blood Volume = red cell volume x 100 x hematocrit-1 x 0.91-1). Subjects will then repeat the above procedures within 10 minutes after completion. Procedures, including volume of CO injected and blood withdrawn, are identical, with the exception of p50 measurements, which will only be done once prior to CO inhalation. The second test is performed to establish a low test-retest variable as it minimizes biological variation that would occur between days. If these two tests yield results within 3% then the test is complete. If greater than 3% we will repeat the 2 tests on a different day once CO levels in the blood have returned to baseline (~48 hours). In total, 10 mL of blood will be taken (8mL for Hb mass - 4mL for each test, and 2mL for p50). CO level in the blood is not expected to exceed 20% following the second test. If it does, subjects will breathe 100% oxygen for 10 minutes. p50, the partial pressure of oxygen when Hb is 50% saturated with oxygen, is calculated using pre-rebreathe values for pH, PvO₂, PvCO₂, Hb concentration, HbO₂, and HbCO. Hb mass will be measured in this manner, i.e., duplicate tests, at baseline day 6 and on days 1, 7, and 13 at high altitude. p50 will be measured on every day Hb mass is measured, as well as on baseline day 3 and day 3 at high altitude when Hb mass is not measured. On p50 only days, one 2mL blood sample will be taken to measure p50, but no Hb mass measurement will be made.

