3 weeks until departure		Saline Saline EPO		Saline Saline EPO		Saline Saline EPO	
2 weeks until departure		Saline Saline EPO		Saline Saline EPO		Saline Saline EPO	
1 week until departure		Saline Saline EPO		Saline Iron EPO		Saline Saline EPO	Departure

Rucksack carry: Subjects will be instructed to complete a 3.1-mile uphill hike as fast as possible while carrying a 35-pound backpack. We previously developed this test to simulate military style field operations for another DoD funded study. The course follows a rugged hiking/jeep trail that begins in a wooded area at ~10,500 feet and ends on a ridge above tree line at ~12,500 feet. Subjects will hike the course as a group after the 5k run first day at high altitude to familiarize themselves with the terrain. The following morning (2nd day) they will be asked to complete the course as fast as possible while being timed. Subjects will also run the course on days 8 and 14. Fit subjects, free of AMS, can finish the course in ~60 minutes.

Traveling and accommodations:

Subjects will be transported to Denver, Colorado in groups of 10-20 by commercial airlines or bus and then immediately driven to Leadville or Breckenridge, Colorado by charter buses. The total travel time from baseline to high altitude will be ~8 hours. Subjects will follow a strict regimen of tasks designed to simulate a high level of physical activity at high altitude (10,000 to 14,000 feet) over three days and two nights (acute) followed by 11 additional days of residence at high altitude (chronic exposure) before returning to Oregon on the 14th day.

Subjects will be housed and fed in condominiums in the Leadville or Breckenridge area. All meals will be cooked and served communally. Omnivorous and vegetarian options will be provided. Subjects will sleep in individual beds, but will share quarters and bathrooms (see note below about COVID management in 'COVID-19 exposure scenario'). Caffeine intake will be limited to the equivalent of two cups of coffee per day. Subjects will refrain from taking any non-study related supplements (over-the-counter, prescription, and recreational) or other non-study drugs or alcohol for the duration of the study beginning with baseline studies through the completion of the study. Violation of these policies will yield a subject's data invalid for the whole study, and thus will result in expulsion from the study and prorated payment.

D. Research Population & Recruitment Methods

Participant population

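### Does the 48-hour repeat rule for discordant Hb mass duplicates leave the day-13 value undefined in a way that matters?

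*Combined protocol and SAP*

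**What the plan says.** The paragraph on hemoglobin mass and p50, under the data collection procedures, sets out two CO-rebreathing tests per session. "If these two tests yield results within 3% then the test is complete". If they differ by more, "we will repeat the 2 tests on a different day once CO levels in the blood have returned to baseline (~48 hours" afterwards. The same paragraph schedules duplicate tests at baseline day 6 and altitude days 1, 7 and 13.

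The end of the altitude stay is fixed elsewhere. Under the late high-altitude measures, "On the morning of day 14, subjects will participate in the rucksack carry", followed by the drive to Denver and the flight home. The travel section has subjects living at altitude "before returning to Oregon on the 14th day". The post-altitude visit is there "to repeat the 5k run and blood draw only", and the blood-volume table in the risk section shows no Hb mass draw at that visit.

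The text gives no exception for day 13. It also does not say how a pair of tests, concordant or discordant, becomes one analysed value.

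**The concern.** Aim 2 asks about acute and chronic changes in Hb mass, and day 13 is the only late measurement of it. Read literally, a discordant day-13 pair never becomes a complete test, cannot be repeated, and has no stated value. Someone would have to choose between the first test, the mean of the two, or treating the value as missing, and could do so after seeing results. If discordant pairs on days 1 and 7 were replaced by repeats while those on day 13 were not, the value would also be built differently at the time points being compared.

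The earlier visits seem to have their own obstacles. A repeat after day 7 falls on day 9, which the schedule describes as free of research activities. A repeat after day 1 falls on day 3, about which the protocol says "On p50 only days, one 2mL blood sample will be taken to measure p50, but no Hb mass measurement will be made". The altitude blood total of about 213 mL equals 3 × 71 mL, which leaves nothing for a repeat.

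**Working it through.** **1. Calendar.** Test day plus 48 h (2 days), with departure on day 14:

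| Test day | Repeat day | Still at altitude? |
|---|---|---|
| 1 | 3 | yes |
| 7 | 9 | yes |
| 13 | 15 | no |

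The repeat is impossible only after day 13. A test later in Eugene would be a post-descent value, not a late-altitude one.

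**2. Could it be done on day 14?** The inputs come from the Hb mass risk paragraph: HbCO rises from about 2% to about 15% (13 points), and the half-life without oxygen therapy is 5 h. The excess over baseline after h hours is 13 × 2^(−h/5):

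- 10 h: 3.25 points
- 12 h: 2.46 points
- 14 h: 1.87 points
- 24 h: 0.47 points
- 48 h: 0.02 points

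A morning repeat after an evening test would start above baseline. The evening timing is partly inferred. It is stated for day 1 ("In the evening, subjects will have an IV placed and venous blood drawn, and will perform Hb mass & p50 measurements"), and day 13 is described only by "This day will be a repeat of day 1 at altitude". By 24 h the excess is small, so a late day-14 repeat is ruled out by the departure and the stated 48 h rather than by washout alone.

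**3. How often would a pair be discordant?** The documents give no test-retest error, so the single-test CV is an assumption. With independent normal errors, the difference of two tests has SD CV × √2, and P(difference > 3%) = 2Φ(−3/(CV√2)). For the 80 subjects selected at performance stabilization, assuming none has withdrawn by day 13:

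| Assumed CV | P(discordant) | Expected of 80 | P(at least one) |
|---|---|---|---|
| 0.7% | 0.2% | 0.2 | 18% |
| 0.8% | 0.8% | 0.6 | 47% |
| 1.0% | 3.4% | 2.7 | 94% |
| 1.5% | 15.7% | 12.6 | near 100% |
| 2.0% | 28.9% | 23.1 | near 100% |

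The count runs from almost none to more than a quarter of subjects, depending on a figure that the documents do not supply.

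**4. Is the mean of a discordant pair a worse measurement?** Let the two tests have independent errors with the same variance s². The covariance of their sum and their difference is s² − s² = 0. Under normality the mean is therefore independent of the difference, and selecting pairs on the difference leaves the mean's distribution unchanged. Its SD is CV/√2, which at CV 1.5% is 1.5/1.414 = 1.06%. A simulation of 2 million pairs gives the same SD for concordant and discordant pairs: 0.71%, 1.06% and 1.42% at CVs of 1%, 1.5% and 2%.

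The result changes if some tests fail technically. With 5% of tests at CV 5% and the rest at 1.5% (assumed), the SD of the mean is 1.91% for discordant pairs and 1.10% for concordant ones.

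**5. What would a written rule change?** At day 13 there is no repeat with or without it. The data in hand are two same-day tests, and the usual value from duplicates is their mean. Under the assumptions of step 4 that mean has the same expectation and SD as the mean of a concordant pair.

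**The case for a change.** The best case for a change is that the plan contains an instruction that cannot be carried out at a named time point of a named outcome, and that a sentence or two before data collection would settle it. Stating one rule for all visits (the same-day mean, with the 3% limit as a flag and a sensitivity analysis without flagged pairs) costs no extra tests and removes a choice that could otherwise be made late.

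The calendar conflict stands, and so does the absence of a written value rule. That absence is general, though: the documents do not define the value for a concordant pair either, so day 13 is one instance of ordinary missing detail. The supporting conflicts are weaker. The text on days without research activities and on p50-only days can be read as describing the routine schedule, to which a triggered repeat is an exception. The blood total also omits the scheduled 2 mL p50 draw on altitude day 3, so it says little about unscheduled draws.

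The one part of the proposed rule that would alter practice is to confine permitted repeats to a sensitivity analysis so that every visit uses the first pair. That buys consistency between visits but gives up the repeat as quality control. Control matters most when some tests fail technically, which is where flagged means are noisier (1.91% against 1.10%). Either choice is defensible.

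**Conclusion.** No change is called for. The 48-hour repeat cannot be done after day 13, and the documents do not say what value a discordant pair then takes. The gap is one that analysts fill sensibly with the mean of the two tests already done. Nothing in the protocol tells them to discard the pair. The lost repeat falls on all arms alike, and no bias between arms is shown. Under independent, normal, equal-variance errors there is no loss of precision compared with concordant pairs (1.06% in both at CV 1.5%).

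The possible mismatch between visits depends on repeats actually being used on days 1 and 7, and its effect has not been quantified. The number of affected subjects, from 0.2 to 23 of 80 over assumed CVs of 0.7% to 2%, rests entirely on those assumptions. The conclusion would weaken if technical failures were common, because flagged means would then be noisier. Even then no day-13 repeat could be obtained within the planned stay, and a more elaborate rule would trade consistency for quality control rather than give a clear gain.

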Intravenous catheter and venous blood draw: We will place a 20-22 gauge (small diameter) IV into a vein in the subject's arm. This IV will be used to for various tests – blood draws for Hb mass & p50, blood draws to measure various biomarkers in the blood, iron/saline infusion during drug treatment, and for contrast bubble injections during ultrasound measures at sea level.

Venous blood draw: Blood for measuring biomarkers will be drawn from an IV (60 mL per blood draw) and centrifuged, and de-identified plasma and serum stored at -80°C until assayed. Additionally, blood will be drawn for baseline iron, transferrin, ferritin, complete blood count, and basic metabolic panel analysis (via QUEST diagnostics, 25 mL) on baseline day 1, and blood will be drawn for sickle cell screening on baseline day 6 (via QUEST diagnostics, 5 mL). Intravenous blood for biomarker analysis will be drawn on baseline 6, and on the second day of iron or saline infusion

to minimize the number of needle sticks. Blood will also be drawn days 1, 7, and 13 at high altitude, and at sea-level post altitude. 60 mL of blood will be drawn for biomarker analysis on each of these blood draw days.

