
Blood measures: Blood samples will be used to measure biomarkers such as soluble transferrin receptor, ferritin, hepcidin, erythropoietin, C-reactive protein, erythropoiesis agents (ESAs), hemoglobin, hematocrit, red blood cell count, reticulocyte number, reticulocyte percentage, mean corpuscular volume, mean corpuscular hemoglobin, CD71/Band3, cytokines including interleukins (IL) -1 β , 6, 8, 10, 12p (70), 17A, 18, 23, and 33, interferons - α 2 and - γ , tumor necrosis factor- α , monocyte chemoattractant protein-1, nitric oxide synthase, endothelin-1, myoglobin, matrix metalloproteinases 2 and 9, cystatin C, myeloid-related protein 8/14, osteopontin, neutrophil gelatinase-associated lipocalin, myeloperoxidase, serum amyloid A, insulin like growth factor binding protein 4, intracellular adhesion molecule 1, and vascular cell adhesion protein 1. Serum will also be collected for Luminex analysis of genetics and metabolism regarding inflammation which will include many of the previously mentioned markers. Additionally, serum will be saved for cell culture experiments in which endothelial and vascular smooth muscle cells will be exposed to serum, these cells will be analyzed for mechanistic changes involving inflammation and health status change of the cells.

Plasma, buffy coat, and serum samples will all be stored for later use; however, these samples will be unidentifiable, only stored with an ID number that will indicate which treatment the sample had been exposed to.

Abnormal blood test results will be shared with participants with a recommendation to see their physician.

Dried Blood Spot Sampling: We will use a commercially available and FDA-approved for patient use blood spot single-use disposable sampling device (TASSO, TASSO Inc, Seattle, USA). The device adheres to skin which has been cleaned with isopropyl alcohol with a light adhesive. Upon activation, a vacuum forms and a lancet pricks the surface of the skin. The vacuum draws blood out of the capillaries and into the sample pod attached to the bottom of the device, collecting 4 samples of 20 microliters (0.020 mL) each over the course of 5 minutes and storing the samples on a dried blood spot card contained within the device. After collection, the device is removed from the skin, the sample card separates from the device and is submitted for analysis. Samples will be taken every time a venous blood draw is taken at sea level (baseline 6, and post dosing) and altitude (day 1, 7, and 13).

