Before all tests, the subject will be telephoned or e-mailed (depending on preference) or told in person (while in Colorado) to confirm participation, remind them of the activities that will take place, checking for questions, and confirming continued interest and as a reminder to: 1) stay hydrated by drinking at least 2 liters of water a day, and 500 ml the morning of the test day; 2) to limit caffeine intake to the equivalent of two 8 oz cups of coffee a day; 3) limit exercise to that prescribed in the study design; with no exercise the day before the VO2Max, APFT and 5K tests; and 4) for exercise tests to time their eating so 1-2 hrs elapse between last meal and heavy exercise (VO2Max, 5K run or ruck hike). In addition, subjects will be emailed (while in Oregon) or reminded in person (while in Colorado) to complete their COVID-19 compliance survey prior to arriving to the lab.

A copy of the consent will be posted after the trial is closed to recruitment and no later than 60 days after the last visit by any subject in this study.

F. Provisions for Participant Privacy and Data Confidentiality

Each subject folder will be stored in locking file cabinets inside the primary investigators' locking offices ([name], [name], [name], or [name]). All other computer files associated with the subject will be identified only through their unique subject ID and stored on password protected lab computers. The de-identified data will be kept for at least 7 years after publication, per NIH guidelines. In the unlikely event the data are not published, they will be kept for at least 10 years after collection. This will ensure sufficient time for publication after data have been collected considering some trainees take up to 6 years to graduate, and often publication does not occur until many years after graduation.

Each subject will be assigned an ID using a random number code system consisting of three to five letters describing the study (e.g., COAST) and a random, non-repeating number (1-1000). This ID will be associated with their data folder, which will contain all study documents and data collected including all associated forms (i.e. informed consent document).

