The PI will maintain a subject ID key capable of identifying subject IDs to subject names and contact information to provide us with the ability to identify subjects as additional questions or research findings arise. This ID key will be kept in a locked filing cabinet also within the office of the primary investigator. No contact information will be stored with subject data.

De-identified data may potentially be shared with other investigators for research purposes.

Specimens collected for research will be de-identified using the subject's unique ID and stored at the University of Oregon until future analysis. Blood collected to be analyzed by a third party (QUEST diagnostics) will be labeled with the subject's ID and birthdate, as required by QUEST, and results from those tests will be available only to members of the [name] lab who have access to the password protected QUEST Quantum online platform. No subject names are included online or on their specimens, and all specimens get destroyed after analysis.

G. Potential Research Risks or Discomforts to Participants

Confidentiality:

If data is lost or stolen, subjects could experience invasion of privacy. To minimize the potential invasion of privacy, we are not collecting social security numbers so that the potential economic impact is greatly minimized. All of our files will be kept in a locked filing cabinet to prevent theft and

data will be de-identified. Data acquired on computers will be password protected. As such, the **probability** of the adverse outcomes discussed above is low, and the **severity** is minimal.

Psychological:

For the echocardiography tests, female subjects will need to have no sports bra on to allow for imaging of the heart and the placement of small electrodes on the chest to record heart rate. To avoid any discomfort, subjects will be given a large, loose-fitting shirt (provided by researchers) to cover up. Male subjects will either go shirtless or be given a loose-fitting shirt. As such, the **probability** of the adverse outcomes discussed above is low, and the **severity** is minimal.

Physiological:

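### One sentence on stored blood samples can be read as showing the treatment arm on the label, and it does not match the random specimen ID described in Section F

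*Combined protocol and SAP*

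**What the plan says.** Three parts of the combined protocol and SAP bear on how stored blood is labelled.

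- **Section C, Blood measures.** Plasma, buffy coat and serum are kept for later use. They are described as unidentifiable and "only stored with an ID number that will indicate which treatment the sample had been exposed to". The same paragraph sends stored serum into cell-culture experiments, of which it says "these cells will be analyzed for mechanistic changes involving inflammation and health status change of the cells".
- **Section C, Venous blood draw.** Blood for biomarkers is centrifuged, with "de-identified plasma and serum stored at -80°C until assayed".
- **Section F, privacy and confidentiality.** "Each subject will be assigned an ID using a random number code system": a short study prefix and a random number between 1 and 1000. The section adds: "Specimens collected for research will be de-identified using the subject's unique ID". On linkage it says "The PI will maintain a subject ID key capable of identifying subject IDs to subject names and contact information", and "This ID key will be kept in a locked filing cabinet".

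On blinding, the Drug intervention paragraph calls the design single-blind and explains how subjects are kept unaware of their arm. It says nothing about laboratory staff or outcome assessors.

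**The concern.** A random number cannot by itself indicate treatment. The Blood measures sentence and Section F therefore do not describe the same label, unless the word *indicate* refers to something outside the label.

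If the label does show the arm, staff who run the assays and cell-culture work could know the allocation while they produce the results. Molecular markers of hypoxia exposure belong to specific aim 2, and Section A adds a search for markers that reveal use of each compound. Knowledge of the arm can sway decisions on repeat runs, handling of outliers and, above all, any reading that needs judgement. The cell-culture readout is the clearest candidate, because the plan does not specify how a change in cell health is to be assessed. Automated measurements such as the Luminex panels leave less room for influence.

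**Working it through.** The plan states no figure on this point and there is nothing to calculate. The check is a comparison of the texts.

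**1. What each part says about the identifier.**

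| Place | Material | Identifier | Treatment element? |
|---|---|---|---|
| Blood measures | Stored plasma, buffy coat, serum | An ID number | Yes, on a literal reading |
| Section F, ID construction | Subject and data folder | Study prefix plus random number | None described |
| Section F, specimens | Research specimens | The subject's unique ID | None described |
| Section F, key | Link from ID to person | Names and contact details | Not mentioned |

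The first row agrees with the others only if the sentence means linkage and not the content of the label.

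**2. Could the subject ID itself carry the arm?** Probably not. Section F says blood sent to the outside laboratory is labelled with the subject's ID, and that blood is first drawn on baseline Day 1. The Day 5 repeat run is meant to help match the groups, and dosing comes after the baseline tests. The ID thus appears to exist before assignment. This is an inference from the order of visits; the plan does not state when IDs are issued. If it is right, the sentence implies either a second code that reflects the arm or a separate list from which the arm can be looked up. The plan describes neither explicitly.

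**3. Would the label be visible before the result exists?** For plasma and serum, yes: Venous blood draw has them stored before they are assayed. The sentence does not cover dried blood spots, so nothing follows for those.

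**4. Does a visible arm contradict a stated blind?** No. The only blinding described is that of subjects.

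**5. How much bias could follow?** The documents do not specify the cell-culture readout, who performs it, or how much it depends on judgement. No estimate can be derived from them, and a count of samples would not measure bias.

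**The case against.** The strongest reply is that there is no conflict. The sentence is about privacy, and its purpose is to say that samples carry no personal identifiers. Section F ties the subject ID to a data folder that holds all study documents and data, so a random ID can lead to the arm without displaying it. The key that Section F describes exists for re-contact, so its silence on treatment is unremarkable. A randomised trial with arm-specific dosing needs an allocation record in any case. The sentence also speaks of the treatment of the *sample*, which might mean its condition or time point. Even a code that reflected the arm need not be readable without a codebook.

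This reply has force. The linkage reading is plausible, and a reader who concludes that laboratory staff *will* see the arm goes further than the documents allow. But the linkage reading is not stated either, and the words as they stand permit the literal one.

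A second reply is that laboratory masking was never promised. That is correct. A reader might infer that the trial's blind is compromised; the documents do not support this, because the design is single-blind and only subjects are said to be blinded. The reply does not remove the point, since masking samples from the people who assay them is compatible with a single-blind design.

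A third reply is that masking may achieve little. ESAs, erythropoietin, ferritin and reticulocytes may reveal the arm whatever the label says. If the people who run the assays also give the injections, a neutral label would not blind them, and the documents do not say whether they do. Both limits stand. They reduce the gain but give no reason to put the arm on samples intended for cytokine or cell-culture work.

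**Conclusion.** The point holds as a minor inconsistency with a cheap remedy. Blood measures and Section F describe the specimen identifier differently, and the text does not settle whether the arm is shown on the label or only traceable through the study record. On the literal reading, there is an avoidable risk of assessment bias in the molecular and cell-culture results, mainly where a readout needs judgement. On the linkage reading, only the wording needs repair.

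The size of any bias cannot be computed. The conclusion rests on two assumptions: that the stored plasma and serum in Blood measures are the material later assayed, as Venous blood draw indicates, and that at least some readouts leave room for judgement, which the plan neither states nor rules out. It does not show that any blind is broken, that staff will know the arm, or that any result would be biased.

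**What to change.** 1. Label stored plasma, buffy coat and serum with the Section F random ID and the time point only.
2. Keep the treatment list from staff who run the assays and cell-culture experiments until the assays are complete and the data are locked.
3. Reword the Blood measures sentence to match Section F. If it was meant to say that the ID can be linked to treatment through the study record, say so and name the record. If it referred to the sample's condition or time point, say that instead.

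It would also help to add a line on whether the people who assay the samples take part in dosing, so that readers can judge how far the masking reaches.

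The cost is a change of wording and labels and some minor key handling. Section F already provides for an ID key in locked storage, so holding a treatment list separately should add little.
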